32. Transnational Research.....	19
33. Drugs or Devices	19
Checklist Section	20

PROTOCOL TITLE: “Evaluating the efficacy of micro-fragmented adipose tissue and intra-articular corticosteroid injections for symptomatic knee osteoarthritis: a randomized, placebo controlled study”

1. Objectives

- 1.1. *The purpose of this study is to evaluate the possible benefits of reduced joint pain and increased joint functionality in participants with knee osteoarthritis after the injection of Lipogems®. Based on limitations of prior research, intra-articular corticosteroids are included as a study group to be evaluated for impact on pain relief and joint functionality in comparison to placebo.*
- 1.2. *We hypothesize that participants who receive an injection of Lipogems® will experience a decrease in pain of the affected knee and an increase in joint functionality in comparison to placebo. We also hypothesize that participants who receive an intra-articular corticosteroid will experience decreased pain or improved functionality in the affected joint.*

2. Background

- 2.1. *Osteoarthritis (OA) causes patients considerable joint pain and leads to instability, reduced range of motion, and functional limitations. Pathologic findings of OA include decreased articular cartilage, joint space narrowing, osteophytes, subchondral sclerosis and bone cysts.¹ Currently, treatment options are confined to symptom management only. Options for treatment include: topical preparations, nonsteroidal anti-inflammatory drugs (NSAIDs), intra-articular injections, and, in severe cases, total knee arthroplasty. Review of recent recommendations shows limitations to all available treatments. Oral NSAIDs have shown relief, but is limited to patients without risk factors or contraindications. Topical NSAIDs are recommended in elderly patients or those with GI risk factors, rather than oral NSAIDs. However, pain improvement took 12 weeks and was not long-lived, potentially due to compliance issues in application.^{2,3} A recent systematic review of intra-articular corticosteroids reported that, due to low-quality evidence, it is inconclusive whether intra-articular corticosteroids provided any short or long-term pain relief.⁴ Taylor's review of hyaluronic acid treatment is hampered by the variability of preparations currently on the market and shortage of double-blind placebo controlled studies, but conflicting data is reported.³ Osteoarthritis Research Society International currently recommends corticosteroid injections for short-term pain relief only, and is inconclusive in recommending hyaluronic acid.⁵ The aforementioned treatment limitations have generated interest in alternative options to restore function and alleviate joint pain, some with the aim of healing damaged articular cartilage. It is well known that articular cartilage is avascular and lacks innervation, which limits its intrinsic healing and repair capabilities. Chondrocytes, derived from MSCs, have limited potential to replicate, which also limits the intrinsic healing and repair capabilities of articular cartilage.^{6,7} The stromal vascular fraction, containing adipose derived mesenchymal stem cells (MSCs), has historically been isolated successfully via enzymatic processes.⁸ There has been preliminary support in the literature for*

PROTOCOL TITLE: “Evaluating the efficacy of micro-fragmented adipose tissue and intra-articular corticosteroid injections for symptomatic knee osteoarthritis: a randomized, placebo controlled study”

reduced pain and improved functional performance in patients who received MSCs as part of treatment.^{7,9,10} However, approaches to isolate MSCs are costly, time consuming, require extensive lab equipment, and are currently limited by complex regulatory issues.¹¹⁻¹³

Thus, interest in an alternative isolation method lead to the development of Lipogems®. Lipogems® is a technique to harvest, process, and inject minimally manipulated adipose tissue. This procedure is enzyme free and requires no clonal expansion or manipulation. Lipoaspirate is harvested and washed in saline solution, then processed through a closed-system device that micro-fragments the adipose tissue. This mechanical process retains the vascular architecture, mature pericytes, and MSCs for autologous injection.^{12,13} As new technologies are becoming available for the treatment of OA, it is important that we gather high-quality data on their efficacy and outcomes. The goal of this study is to evaluate the possible benefits of reduced joint pain and increased joint functionality in participants with knee osteoarthritis after the injection of Lipogems®. In addition, given the limitations of prior research on the efficacy of intra-articular corticosteroids, we will also include this as an additional study group to compare to placebo. Although Lipogems® is relatively new to the United States, it has been used for a variety of orthopaedic arthroscopic applications overseas including the treatment of knee OA and is being used more frequently now in the United States. As of now, there are no published studies reporting the outcomes of patients who receive Lipogems® for knee OA. There have been case reports published showing favorable outcomes. Thus, this would be the first study reporting data on the efficacy of Lipogems® for pain relief in knee OA in a randomized, controlled clinical trial with a larger sample of participants. It would also be the only study to date comparing Lipogems® to intra-articular corticosteroids and placebo injections. We feel this study design will provide new insight into the efficacy of Lipogems® for pain relief of symptomatic knee OA as well as offer new data on the efficacy of intra-articular corticosteroids in this application.

- 2.2. *We do not have any preliminary data. There is, at this point, no study published explicitly evaluating the efficacy of Lipogems in patients with knee osteoarthritis, although Lipogems® has been used for this purpose and is acknowledged in case reports. One case study by Striano et al reports decreased knee pain and no adverse side effects following injection of Lipogems®.¹⁴*
- 2.3. *Estimates say that there are between 15-27 million US adults age 25 or older with clinical OA of at least one joint, and that 49.7% of people over the age of 65 report that they have diagnosed arthritis.¹⁵⁻¹⁷ The lifetime risk of symptomatic knee osteoarthritis is estimated to be 13.8%, and an even higher risk is identified for obese persons (19.7%) and females (16.3%).¹⁸ OA is not exclusive to patients over 65. Recent estimates show that approximately 6.6 million people between the ages of 45-64 had OA in 2011-*

PROTOCOL TITLE: “Evaluating the efficacy of micro-fragmented adipose tissue and intra-articular corticosteroid injections for symptomatic knee osteoarthritis: a randomized, placebo controlled study”

2012. Furthermore, it is estimated that 1.7 million adults under the age of 45 had OA in the same year.¹⁷ Thus, the burden of OA is much more widespread than the elderly population.

Current therapies are limited to symptom management only, none curative or capable of stopping the progress of disease. Thus, a staggering number of Americans of all ages are living with a chronically painful joint condition.

Furthermore, with the burden of an aging population and high rate of obesity in the United States, the management and treatment of OA will continue to be an important health concern.

As new technologies are becoming available for the treatment of OA, it is important that we gather high-quality data on their efficacy and outcomes. The goal of this study is to evaluate the possible benefits of reduced joint pain and increased joint functionality in participants with knee osteoarthritis after the injection of Lipogems®. In addition, given the limitations of prior research on the efficacy of intra-articular corticosteroids, we will also include this as an additional study group to compare to placebo. This would be the first study to evaluate the efficacy of Lipogems® for pain relief in knee OA in a randomized, controlled clinical trial with a large sample of participants. It would also be the only study to date comparing Lipogems® to intra-articular corticosteroids and placebo injections. We feel this study design will provide new insight into the efficacy of Lipogems® for pain relief of symptomatic knee OA as well as offer new data on the efficacy of intra-articular corticosteroids for this application. .

3. Study Design

- 3.1. This study will be conducted as a randomized, placebo-controlled clinical trial. Participants will be randomized to receive either Lipogems®, intra-articular corticosteroids, or a placebo injection of saline. Lipogems® is cleared for use by the FDA in orthopaedics and arthroscopy and is offered as a treatment option for knee osteoarthritis. This study will be evaluating the effectiveness (not safety) of Lipogems® when compared to corticosteroids and placebo. Thus, no information will be submitted to the FDA.
- 3.2. It is not feasible to blind participants who are randomized to receive Lipogems® as adipose tissue must be obtained from the participant. However, participants randomized to receive intra-articular corticosteroids or placebo injections will be blinded.
- 3.3. Randomization will be stratified according to baseline pain severity as defined here, ethnicity, and age to ensure a balanced assignment across the three groups with respect to important determinants. Stratification will not be based on radiographic severity as previous studies have shown no correlation between the radiographic severity of knee osteoarthritis and the pain experienced by the patient.

4. Inclusion and Exclusion Criteria

PROTOCOL TITLE: “Evaluating the efficacy of micro-fragmented adipose tissue and intra-articular corticosteroid injections for symptomatic knee osteoarthritis: a randomized, placebo controlled study”

- 4.1. Participants will be recruited from the patient population at the clinics of [name], [name], [name] and [name], PA-C at the University of New Mexico’s Orthopaedic Department. Since all potential participants will be independently seeking care for osteoarthritis, the participating clinicians and research staff will screen the patients for inclusion criteria during their standard examination. Qualifying patients will be offered enrollment into the study at that time.
- 4.2. Inclusion criteria include being the age of eighteen or older, diagnosed symptomatic knee osteoarthritis, and radiographic evidence of knee osteoarthritis. For the purposes of this study, radiographic evidence of knee osteoarthritis is defined as any one or more of the following: osteophytes, joint space narrowing, loss of articular cartilage thickness, subchondral sclerosis or cysts. Patients will also meet inclusion criteria if their intake sheet pain score is at least a 3 out of 10, as pain scores less than 3 are unlikely to show a clinically meaningful improvement from any treatment option. Patients will be excluded from the study if they have a history of treatment with any intra-articular knee injection or have current ligament instability as demonstrated by a positive Lachman Test, Anterior or Posterior Drawer Test, or positive Valgus or Varus Stress Test.¹⁹ Patients with a known allergy to lidocaine will also be excluded from the study. Patients will be excluded if they do not meet our above-mentioned severity criteria with a pain score of at least 3 on the intake sheet.
- 4.3. This study will only include English or Spanish speaking adults over the age of eighteen who are capable of independently consenting to participate in a research study. This study will not include any children, pregnant women, or prisoners. Women of childbearing age will be included only after they have had a negative urine pregnancy test at point of care.
- 4.4. Individuals under the age of 18 will be excluded from this study. As osteoarthritis is largely considered a degenerative joint disease, this population is highly unlikely to have osteoarthritis of the knee and thus will not be eligible for the study.

5. Number of Subjects

- 5.1. This study will take place solely at the University of New Mexico Hospital.
- 5.2. Based on our power analysis, we need 75 participants to complete the study. All subjects will have been pre-screened for eligibility by the participating clinicians.
- 5.3. We will take advantage of the 5-repeated measurements of joint pain and functionality from each patient, and compare the post-treatment trajectory of joint pain and functionality over follow-up between a pair of treatment groups. This approach facilitates group comparisons (1) at individual follow-up times, (2) life course of effects over the entire follow-up period. This will be done by means of mixed-effects regression models which incorporate both within-patient

PROTOCOL TITLE: “Evaluating the efficacy of micro-fragmented adipose tissue and intra-articular corticosteroid injections for symptomatic knee osteoarthritis: a randomized, placebo controlled study”

(over time) and between-patient variations, and are more flexible in making inference on group differences. The method also allows for the inclusion of multiple covariates (see below) in the model to quantify effects attributable to the treatments. We will also consider repeated measurement analysis of covariance and pairwise comparison (e.g. t-tests) to validate our analysis with respect to robustness and sensitivity. We will follow LaPrade’s recent recommendations of minimal reporting requirements for treatments that potentially include mesenchymal stem cells, such as Lipogems®. This includes age, gender, diabetes status, inflammatory conditions, pre-existing joint problems, and current NSAID use.¹⁹ Since patient perception of post-treatment pain as measured by the VAS scale is a main variable of interest in our hypothesis, we searched the literature for previous studies in which the variability of pain using a VAS scale was investigated.²⁰⁻²³ We estimated that the standard deviation likely to be found for our own observations will be approximately 35 on a 100 point scale, conservatively. We assume that most clinicians will consider a difference in post-treatment pain of about 15 points to be clinically important, as supported by Tashjian *et al*, who estimated 1.4 cm as the minimal clinically important difference on a 10 cm scale. To determine an adequate sample size for our pilot, we assumed average change in pain score over the follow-up to be 10-15, and standard deviation to be 10-20. To have 80% power with a 5% Type I error rate, an approximate 2-way ANOVA model suggest sample size in the range of 18-49 per group. We adopt $n=22$ as our minimum sample size per group based on the assumption of 15-point change in pain score over time on average and a 20-point standard deviation over time. Within the recruitment time window, we will aim to enroll $n=25$ or more participants in each of the three treatment arms so long as the logistics permit. We expected the mixed-effect model will increase the power by utilizing the longitudinality of the data, compensating potential loss of power due to drop-outs and serial correlation.

6. Study Timelines

6.1. Describe:

- Individuals who agree to participate in this study will be enrolled during an initial screening visit which they will have independently sought and scheduled. Their participation will involve one procedure visit, two brief follow-up visits, and three online completion of surveys. We anticipate that it will take approximately 15 months from date of enrollment to complete each individual subject’s procedure and follow-up visits, allowing time for flexibility in scheduling based on the clinician and subject’s schedules.
- We estimate that it should take approximately three months to enroll 75 subjects. We anticipate this being feasible based on the four participating clinicians’ current schedules. Roughly, an orthopaedic surgeon may see upwards of 50 patients a day. Approximately 10% of these patients have knee OA and potentially qualify for the study.

PROTOCOL TITLE: “Evaluating the efficacy of micro-fragmented adipose tissue and intra-articular corticosteroid injections for symptomatic knee osteoarthritis: a randomized, placebo controlled study”

- *We anticipate the data analysis to take a maximum of two months following the completion of all data collection.*

7. Study Endpoints

- 7.1. *This study will conclude once all active, enrolled participants have completed their one-year follow-up.*
- 7.2. *Participants will be followed via standard of care and monitored at follow-up appointments. After we have had 10 participants enrolled in each group, we will do a preliminary evaluation of the available data.*
- 7.3. *Not applicable. We will not have exploratory endings.*

8. Research Setting

- 8.1. *Research will be conducted at the University of New Mexico Hospital Orthopaedic Clinics of [name], [name], [name] and [name], PA-C. Research, including all patient visits and procedures, will also be conducted at the CTSC.*
- 8.2. *Participants will be recruited from the patient population at the clinics of [name], [name], [name] and [name], PA-C at the University of New Mexico’s Orthopaedic Department. Since all potential participants will be independently seeking care for osteoarthritis, the participating clinicians and research staff will screen the patients for inclusion criteria during their standard examination.*
- 8.3. *Procedures and follow-up visits will be performed at the CTSC facilities on North Campus.*
- 8.4. *Not applicable. There will be no community advisory board*

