1. Participants will be screened prior to enrollment. Depending on their medical history and prior consultations, they will likely have a physical exam and x-rays of the affected knee(s). This is standard of care and will happen prior to enrollment in the study. X-ray images and medical data from these visits may be used for the purposes of analyzing statistical data.

PROTOCOL TITLE: "Evaluating the efficacy of micro-fragmented adipose tissue and intra-articular corticosteroid injections for symptomatic knee osteoarthritis: a randomized, placebo controlled study"

2. Upon enrollment, participants will be randomized to a treatment group and scheduled for their injection procedure.
3. At their injection visit, participants will complete the Western Ontario and McMaster Universities Osteoarthritis Index, a Visual Analog pain scale, and the Knee Injury and Osteoarthritis Outcome Score scales to establish a baseline. They will also fill out a medication log to document any medications that they take, including oral pain medications, although we will not be intervening with oral medications. They will complete these surveys and the log again at 2 weeks, 6 weeks, 3 months, 6 months, and 1 year after the injections

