4. Participants will receive their assigned injection. Participants who are randomized to the placebo group will receive an injection of 7cc of sterile saline. Participants who are randomized to the corticosteroid group will receive an injection of 2cc (80mg) of Kenalog®-40 (triamcinolone acetonide injectable suspension, USP) mixed with and 5 cc of 1% plain lidocaine for a total of 7cc of fluid injected. Kenalog® injections are part of the current standard of care for patients with osteoarthritis of the knee. Participants who are randomized to the Lipogems® treatment group will undergo a lipoaspiration from their abdomen and autologous injection of the harvested adipocytes into their knee. It is standard to harvest three to four times more adipose tissue than is planned to be injected to account for tissue processing by the Lipogems® device. We plan to inject 7cc of autologous adipose tissue. Thus, we will harvest between 25 and 30 cc of adipose tissue from each patient. The tissue will be processed immediately and 7cc will be injected. Any remaining adipose tissue will be disposed of immediately in biohazardous waste. Lipogems® is currently approved for orthopedic and arthroscopic procedures; thus, this would be an on-label use. All injections will be performed in the clinic by [name], [name], and [name] PA-C as an in-office procedure.
5. Participants will be scheduled to return for in-person follow-up visits with a research staff member at 6 weeks and 6 months after their injection, where they will again complete a medication log, Western Ontario and McMaster Universities Osteoarthritis Index, a VAS pain scale, and the Knee Injury and Osteoarthritis Outcome Score scales. They will also complete the above surveys and log at 2 weeks, 3 months, and 1 year post injection, but these will be completed online. The above mentioned surveys and medication log will be generated in RedCap and emailed securely to participants for their completion. If participants do not have email or access to the internet, these surveys will be completed over the phone and entered into RedCap by research staff.
6. Upon completion of their 1-year questionnaires, participants who were randomized to receive Lipogems® or Corticosteroid injections will be finished participating in the study.

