- 25.1.24. *Not applicable. No permissions from individuals other than the patient will be required as all study participants are required to be eighteen years of age or older and capable of providing legally effective consent.*
- 25.1.25. *Not applicable. Children will not be enrolled in this study.*
- 25.1.26. *Not applicable. Children will not be enrolled in this study.*
- 25.1.27. *Not applicable. Children will not be enrolled in this study.*

26. Documentation of Consent

- 26.1. *This study will utilize an informed consent document in order to maintain documentation that the patient has given consent to participate in the study.*
- 26.2. *Not applicable. This study will not require the use of stored tissue samples.*
- 26.3. *Consent for this study will be obtained verbally and in-person by the participating clinicians, medical students, or research staff.*

PROTOCOL TITLE: “Evaluating the efficacy of micro-fragmented adipose tissue and intra-articular corticosteroid injections for symptomatic knee osteoarthritis: a randomized, placebo controlled study”

27. Study Test Results/Incidental Findings

- 27.1. **Individual Results:** Participants will be made aware of any physical findings in-person at their follow-up visits. Participants will still be kept blinded to their treatment group, as this is a single-blinded study. Once they have completed their one year follow-up questionnaire, the participants will be unblinded and those in the placebo group will be offered the opportunity to cross-over and receive a corticosteroid injection.
- 27.2. **Incidental Findings:** We do not anticipate coming across any incidental findings. If found, they will be disclosed to the patient.

28. Sharing Study Progress or Results with Subjects

- 28.1. Not applicable. Subjects will not be provided with trial progress while the study remains underway.
- 28.2. Participants will be made aware of what arm of the study they were assigned to. Lipogems® participants will have known since assigned to that group, as the procedure cannot be blinded. However, as this is a single-blinded study, placebo and corticosteroid participants will be made aware of their treatment at the conclusion of the study. Placebo participants will be given the option to receive a corticosteroid injection after they complete their 1 year questionnaire.

29. Inclusion of Vulnerable Populations

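### Lipogems is compared open-label on self-reported outcomes, so saline is a masked placebo only for corticosteroid, and the plan sets no matching limit on the Lipogems claim

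*Combined protocol and SAP*

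**What the plan says.** - **Claim.** The first hypothesis, in section 1.2, is that Lipogems participants "will experience a decrease in pain of the affected knee and an increase in joint functionality in comparison to placebo". Section 3.1 says "This study will be conducted as a randomized, placebo-controlled clinical trial". The title carries the same label and speaks of efficacy.
- **Blinding.** Section 3.2 says "It is not feasible to blind participants who are randomized to receive Lipogems® as adipose tissue must be obtained from the participant", and continues: "However, participants randomized to receive intra-articular corticosteroids or placebo injections will be blinded". Section 28.2 adds that "Lipogems® participants will have known since assigned to that group, as the procedure cannot be blinded". Section 27.1, by contrast, says "Participants will still be kept blinded to their treatment group, as this is a single-blinded study", with no exception for the Lipogems arm.
- **Procedures.** In section 12.1, step 4, "Participants who are randomized to the placebo group will receive an injection of 7cc of sterile saline". The corticosteroid arm also has a knee injection only. The Lipogems arm has an abdominal lipoaspiration as well as the knee injection. No sham harvest is described.
- **Outcomes.** Section 12.1, steps 3 and 5, lists WOMAC, VAS pain and KOOS. All three are participant questionnaires, and section 13.2 names perceived pain on the VAS as a main variable.
- **Analysis.** Section 13.1 plans pairwise comparisons of trajectories by mixed models, with repeated-measures analysis of covariance and t-tests as checks. It treats all pairs of arms alike and says nothing about how the unmasked comparisons will be interpreted.

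**The concern.** A placebo arm supports a claim of efficacy over placebo when participants in both arms hold the same beliefs about what they received and go through the same procedure. Here that is true of corticosteroid versus saline. It is not true of either Lipogems contrast: one side knows it had the new procedure, the other side knows it did not, and only one side had tissue harvested. Both then rate their own pain and function. A Lipogems-saline difference mixes any effect of the tissue with the effects of the harvest and of expectation, and the planned data cannot separate them. Lipogems versus corticosteroid has the same problem, so the third arm does not rescue the inference.

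At stake is what a positive result may be called. As worded, the plan would let an open-label difference be described in the same terms as the masked one.

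**Working it through.** **1. The three contrasts side by side** (sections 3.2, 12.1 and 28.2)

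| Contrast | Participants masked between these arms? | Same procedure? | What the difference estimates |
|---|---|---|---|
| Corticosteroid vs saline | Yes (3.2, 28.2) | Yes, 7cc knee injection in each | Drug over placebo |
| Lipogems vs saline | No | No, harvest in one arm only | Product + procedure + expectation |
| Lipogems vs corticosteroid | No | No, harvest in one arm only | Difference in product + procedure + expectation |

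The label in the title and in 3.1 fits the first row only. Section 27.1 as written covers all participants and so conflicts with 3.2 and 28.2 for the Lipogems arm. A few pages were not available to this review, so *not described* means not in the text supplied.

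Baseline adjustment would not clear this up. Section 12.1 says "Upon enrollment, participants will be randomized to a treatment group and scheduled for their injection procedure" (step 2), and the baseline questionnaires follow at the injection visit (step 3). Lipogems participants therefore already know their arm when they give baseline scores.

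**2. The plan's own figure**

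Section 13.2 adopts 22 per group for a 15-point change, SD 20, 80% power and 5% type I error. With n = 2[SD(z_α + z_β)/Δ]²:

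- one-sided 5%: 2[20(1.645 + 0.842)/15]² ≈ 22.0, which gives 22 and matches;
- two-sided 5%: 2[20(1.960 + 0.842)/15]² ≈ 27.9, which gives 28.

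The plan does not state sidedness. That is a separate matter, and nothing here depends on it.

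**3. Illustration of what a shift would do**

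Inputs from the documents: 25 per arm as the target (5.3) or 22 as the minimum (5.3, 13.2), and SD 20 or SD 35 (both quoted in 5.3 and 13.2). Assumptions: true Lipogems effect zero; knowledge of treatment moves the VAS difference by B points in favour of Lipogems; two-sided 5%; one two-sample t-test. **The documents give no value for B.**

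Non-centrality δ = B / [SD√(2/n)]. The chance of significance is P(|T| > t₀.₉₇₅), where T is non-central t with 2n − 2 degrees of freedom and non-centrality δ.

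Standard error SD√(2/n):

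- n = 25: 20√0.08 = 5.66; 35√0.08 = 9.90
- n = 22: 20√0.0909 = 6.03; 35√0.0909 = 10.55

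Example: n = 25, SD 20, B = 10 gives δ = 10/5.66 = 1.77 and a 41.0% chance of significance.

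| B (points) | n=25, SD 20 | n=25, SD 35 | n=22, SD 20 | n=22, SD 35 |
|---|---|---|---|---|
| 0 | 5% | 5% | 5% | 5% |
| 5 | 13.9% | 7.9% | 12.8% | 7.5% |
| 10 | 41.0% | 16.8% | 36.7% | 15.3% |
| 15 | 73.8% | 31.8% | 68.1% | 28.4% |

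For any B above zero the chance rises from 22 to 25 per arm. More patients make a biased difference more likely to be significant. The mixed model over the follow-ups does not remove B either, because a systematic shift between arms is part of the estimated group difference.

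**The case against.** - **The plan discloses it.** This stands. Section 3.2 gives the lack of blinding and the reason, next to the placebo-controlled label, and 28.2 repeats it. A reader might infer from 27.1 that the plan claims full blinding, but 28.2, in the following section, limits blinding to placebo and corticosteroid participants. Section 27.1 is loose wording to be reconciled, not concealment. Disclosure still does not limit the inference, and no section does so.
- **Nothing says that a significant result will be declared efficacy.** This also stands. Section 13 has no rule for conclusions, and 1.1 speaks of possible benefits. A reader might infer that the plan commits itself to reporting expectation as efficacy; the text does not go that far. It leaves the way open.
- **Lipogems versus placebo is not designated primary, and the study is a pilot.** Both are correct. The prominence of that comparison rests on order and emphasis in 1.1 and 1.2, and the sample-size text in 5.3 and 13.2 uses the word pilot. A reader might call this a failure of the trial's primary confirmatory test, but the documents name no such test.
- **The percentages are power figures under another name.** In effect they are: they give power at a difference of B. They show the consequence if B exists, not how large it is. B = 15 equals the whole difference that the plan calls clinically important. Saline participants may believe they received corticosteroid, so B is a difference in expectation between arms and may be small. The table also uses one t-test, not the planned mixed model.
- **Blinding is not feasible.** Accepted. The point does not ask for a sham harvest.

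**Conclusion.** The point holds as one about labelling and inference. Both Lipogems contrasts are open-label on self-reported outcomes, saline is a masked placebo only for corticosteroid, and 27.1 conflicts with 3.2 and 28.2. The documents show this without any arithmetic. The corticosteroid-saline comparison is not affected.

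The size of any bias is unknown. For assumed shifts of 5 to 15 points and no true effect, the chance of a significant difference at 25 per arm runs from 14% to 74% at SD 20 and from 8% to 32% at SD 35. These figures are illustrative and should not be read as the trial's false-positive rate.

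This should be fixed, but it does not invalidate the design: the limitation is disclosed, and the remedy changes what may be concluded, not how the trial is run.

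**What to change.** 1. In the title and in sections 1.2, 3.1 and 27.1, confine the terms placebo-controlled and blinded to corticosteroid versus saline. Reconcile 27.1 with 3.2 and 28.2 by stating the Lipogems exception there.
2. In 13.1, before results are seen, state that both Lipogems contrasts are open-label, that they estimate product, procedure and expectation together, and that they will not be reported as efficacy over placebo.

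Two additions that may come to mind are not recommended:

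- *A line giving the bias that would bring the lower 95% limit to zero.* If that limit is L, subtracting a constant B gives L − B, which is zero when B = L. The line only repeats the confidence limit.
- *A pre-randomisation expectation score as a covariate.* It is balanced across arms on average, so adjusting for it cannot remove a bias that arises from knowing the allocation. As an effect modifier at 25 per arm and SD 20, its interaction per SD of expectation would have a standard error of about 20√(2/25) = 5.7 points, too imprecise to help.

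The cost is protocol wording only, with no change to arms, procedures, data collection or sample size. The downside is a more modest claim for Lipogems.
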